10.3.1 Definition of AE

AE Definition

- An AE is any untoward medical occurrence in a patient or clinical study subject, temporally associated with the use of a study intervention, whether or not considered related to the study intervention.
- In clinical studies, an AE can include an undesirable medical condition occurring at any time, including screening or follow-up periods, even if no study intervention has been administered.
- NOTE: An AE can therefore be any unfavorable and unintended sign (including an abnormal laboratory finding), symptom, or disease (new or exacerbated) temporally associated with the use of a study intervention.

Version 6.0 80 of 138 April 11, 2024

Events Meeting the AE Definition

- Any abnormal laboratory test results (hematology, clinical chemistry, or urinalysis) or
 other safety assessments (e.g., ECG, radiological scans, vital signs measurements),
 including those that worsen from Baseline, considered clinically significant in the medical
 and scientific judgment of the Investigator (e.g., not related to progression of underlying
 disease).
- Exacerbation of a chronic or intermittent pre-existing condition including either an increase in frequency and/or intensity of the condition.
- New conditions detected or diagnosed after study intervention administration even though
 it may have been present before the start of the study.
- Signs, symptoms, or the clinical sequelae of a suspected drug-drug interaction.
- Signs, symptoms, or the clinical sequelae of a suspected overdose of either study
 intervention or a concomitant medication. Overdose per se will not be reported as an
 AE/SAE unless it is an intentional overdose taken with possible suicidal/self-harming
 intent. Such overdoses should be reported regardless of sequelae.
- "Lack of efficacy" or "failure of expected pharmacological action" per se will not be
 reported as an AE or SAE. Such instances will be captured in the efficacy assessments.
 However, the signs, symptoms, and/or clinical sequelae resulting from lack of efficacy will
 be reported as AE or SAE if they fulfill the definition of an AE or SAE.

Events NOT Meeting the AE Definition

- Any clinically significant abnormal laboratory findings or other abnormal safety
 assessments which are associated with the underlying disease, unless judged by the
 Investigator to be more severe than expected for the subject's condition.
- The disease/disorder being studied or expected progression, signs, or symptoms of the disease/disorder being studied, unless more severe than expected for the subject's condition.
- Medical or surgical procedure (e.g., endoscopy, appendectomy): the condition that leads to the procedure is the AE.
- Situations in which an untoward medical occurrence did not occur (social and/or convenience admission to a hospital).

Version 6.0 81 of 138 April 11, 2024

 Anticipated day-to-day fluctuations of pre-existing disease(s) or condition(s) present or detected at the start of the study that do not worsen.

Adverse Events of Special Interest (AESI)

- Adverse event of special interest (AESI) is an AE (serious or nonserious) of scientific and
 medical concern specific to the Sponsor's product or program, for which ongoing
 monitoring and notification by the Investigator to the Sponsor is required.
- AESIs may be modified during a study by protocol amendment, which will enable the Sponsor to collect additional information to better assess any potential and identified risks during the development surveillance.
- The role of the DMC in the handling of these AESIs will also be considered.
- The AESI to be defined in this study includes:
 - Galactorrhea is the spontaneous discharge of milk or a milk-like secretion from the breast in the absence of parturition or beyond six months' post-partum in a non-breastfeeding woman. The secretion may be intermittent or persistent, scant or abundant, free-flowing or expressible, and unilateral or bilateral. An inquiry and breast examination can provide important clinical findings of subjects with galactorrhea.
 - Change in menstrual cycles with oligo- or amenorrhea is defined as no bleeding or spotting in a 56- day interval.
 - Hirsutism is a condition in subjects with excessive growth of dark or coarse hair in a male-like pattern —face, chest, abdomen and back.
 - Acne involves whiteheads, blackheads or pimples that usually appears on the face, forehead, chest, upper back and shoulders.
 - Palpitations are feelings of having a fast-beating, fluttering or pounding heart, or single
 forceful or skipped beats that not caused by emotional or physical stimulus, exercise, other
 drugs or food, and cannot be relieved through rest or mental relaxation.
 - Change in mood or behavior includes abnormal thought, speech, and behavior after IMP administration compared with past. Such as mood extremes (depression or mania), new or worsening symptoms of anxiety or depression, and disorganized speech or behavior.

Version 6.0 82 of 138 April 11, 2024

- Infection denotes conditions with immunosuppression. This typically manifests as recurrent, severe, unusual, or opportunistic infections.
- Constant or severe headache that is distinctly different in quality from usual headaches, and may be worse at night or in the early morning, including newly happened or worsening dull, "pressure-type" headaches, sharp or "stabbing" pain. They can be localized to a specific area or generalized. They can be made worse with coughing, sneezing or straining.
 - Change in vision (and particularly loss of peripheral vision) includes dim, dark, or blurred vision or diminished peripheral vision in one or both eyes or double vision or diminished peripheral vision on one or both sides, etc.

Theoretically, PRLR blockage will increase PRL and may impact hormone excretion, however PRLR already has been blocked and it is unlikely increased PRL making functional work. Even though risks are more conceptional but need to monitor carefully during study period.

Symptoms of dopamine withdrawal

By blocking PRLR, HMI-115 will increase PRL secretion which may subsequently trigger dopamine release from hypothalamus. Any symptoms of dopamine withdrawal that have been reported after discontinuation of treatment, including apathy, anxiety, depression, fatigue, sweating and pain should be monitored. Theoretically however, PRLR on the dopamine releasing neuron is blocked, it is very unlikely that dopamine releasing will be triggered.

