8.1 Efficacy Assessments

8.1.1 Electronic-Diary (e-Diary)

All subjects will be administered an e-Diary after adequate training at Visit 2. Subjects are required to record uterine bleeding and endometriosis-associated pain every day at around the same time for the entire duration of the study. The use of rescue medications for endometriosis-associated pain will also be recorded. Compliance to e-Diary filling will be assessed as shown in the SoA (refer to Section 1.3). Subjects need to return the e-diary devices after the completion of study participation or after withdrawal from the study.

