8.1.5 Uterine Bleeding

Subjects will be prompted to indicate if they had "Did you have any uterine bleeding in the last 24 hours (last calendar day)?" Subject will then document the intensity of the bleeding as follows:

0	None	
1	Spotting	A light amount of bleeding noted, no protection or panty shield only
2	Light	1 to 2 regular tampons or pads required in 24 hours
3	Medium	3 to 4 regular tampons or pads required in 24 hours
4	Heavy	More than 4 tampons or pads required in 24 hours

Version 6.0 52 of 138 April 11, 2024

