8.4.2 Method of Detecting AEs and SAEs

The method of recording, evaluating, and assessing causality of AEs and SAEs and the procedures for completing and transmitting SAE reports are provided in Section 10.3.

Care will be taken not to introduce bias when detecting AEs and/or SAEs. Open-ended and non-leading verbal questioning of the subject is the preferred method to inquire about AE occurrence.

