4.3 Menstrual History

Quantitative measurements of historical menstrual cycle and period in days before screening, and menstrual cycle and period in days during study (from informed consent to end of study) will be summarized by treatment group and overall using PAS. Categorical lengths of historical menstrual cycle (<28, ≥28 - ≤ 35, and > 35 days), historical menstrual period (<3, ≥3 - <5, ≥5 - < 7, and ≥ 7 days), menstrual cycle during study (<28, ≥28 - ≤ 35, and > 35 days), and menstrual period during study (<3, ≥3 - <5, ≥5 - < 7, and ≥ 7 days) will also be summarized.

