8.1 Adverse Events

All AEs will be coded using the Medical Dictionary for Regulatory Activities (MedDRA) 24.0 or a later version.

Treatment Emergent Adverse Events (TEAEs) will be tabulated and are defined as those AEs with a start date on or after the first administration of IMP.

Where dates are missing or partially missing, AEs will be assumed to be treatment-emergent, unless there is clear evidence (through comparison of partial dates) to suggest that the AE started prior to the first administration of IMP. For AEs with completely unknown dates, dates will be shown as NK (unknown) in the listings. For AEs with partially start and/or end dates, the available day, month and year components will be shown in listing.

Frequencies and percentages of subjects with TEAEs will be calculated for each treatment group as follows:

- Overview incidence of all AEs
- A summary of the number and percentage of subjects reporting a TEAE by treatment, SOC, and PT
- A summary of the number and percentage of subjects reporting a TEAE by treatment, causality, SOC, and PT
- A summary of the number and percentage of subjects reporting a TEAE by treatment, severity, SOC, and PT
- A summary of the number and percentage of subjects reporting a AESI by treatment, SOC, and PT
- A summary of the number and percentage of subjects reporting a AESI by treatment, causality, SOC, and PT

Adverse event summaries will be ordered in terms of decreasing frequency for SOC, and PT within SOC, in the overall treatment groups, and then alphabetically for SOC, and PT within SOC. The actual version of the MedDRA coding dictionary used will be noted in the AE tables.

For each subject and each adverse event, the worst severity recorded will be attributed and used in the by-severity summaries. Similarly, the worst causality (most related to treatment) will be attributed and used in the by-causality summaries. If severity or causality is missing, a conservative approach for AE assessment (taking into account the worst case) will be followed.

Below listings will be provided:

- A by-subject listing of AEs
- A by-subject listing of AESIs

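### The SAP never applies the protocol's 56-day rule for the oligo-/amenorrhea AESI to the daily bleeding diary, so the event may be under-counted and the cycle summaries can mask it

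*Protocol*

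**What the plan says.** **Definition.** Protocol 10.3.1 lists change in menstrual cycles among the AESIs, with the rule "oligo- or amenorrhea is defined as no bleeding or spotting in a 56- day interval". For AESIs in general, "monitoring and notification by the Investigator to the Sponsor is required".

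**Detection.** Protocol 8.4.2: "Open-ended and non-leading verbal questioning of the subject is the preferred method to inquire about AE occurrence".

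**Data.** Protocol 8.1.1: "Subjects are required to record uterine bleeding and endometriosis-associated pain every day at around the same time for the entire duration of the study". Protocol 8.1.5 grades each day from 0 (none) and 1 (spotting) up to 4 (heavy).

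**AESI analysis.** SAP 8.1 plans "A summary of the number and percentage of subjects reporting a AESI by treatment, SOC, and PT", the same table by causality, and a listing. None of these refers to the diary.

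**Cycle summaries.** SAP 4.3 summarises "menstrual cycle and period in days during study (from informed consent to end of study"; its top length category is more than 35 days. SAP 7.3.6 describes changes in period days, cycle days and mean heaviness at the Week 6, 12 and 24 measurements. SAP 7.2.1 and 7.3.1 define those measurements. When the visit falls outside menses, Weeks 6 and 12 use the closest menses and Week 24 uses the latest earlier one. No maximum distance is given.

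**The concern.** Table 2-1 of the protocol names oligo- or amenorrhea as a possible consequence of raised prolactin, and its mitigation is to collect the event as an AESI. Protocol 2.2 criticises existing drugs because the amenorrhea they induce conflicts with the wish for fertility. A low AESI count would therefore be read as support for the product.

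That count depends on a woman mentioning missed periods, or on the site noticing them and reporting an AE. The daily record that could confirm or exclude the event is not used for this purpose. If the cycle-length summaries also look normal for the same women, nothing in the planned tables would prompt a second look.

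**Working it through.** **1. Can the rule be tested?** Yes. It needs a run of 56 days with neither bleeding nor spotting. The diary asks daily and separates none from spotting. Protocol 10.3.1 does not name the diary as its source, but no other daily bleeding record is planned.

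**2. Does the SAP apply it?** No. SAP 8.1 works from reported AEs, SAP 4.3 has no 56-day cut, and SAP 7.3.6 has no count of bleeding-free runs. Protocol 9.4.5 plans the percentage of days with any bleeding; SAP 7.3.6 does not include it.

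**3. What do the cycle rules show when periods stop?**

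Inputs from the documents: eligible cycles of 21 to 35 days (Protocol 5.1); first dose on cycle days 1 to 5 (SoA note 3); visits at Days 43, 85 and 169 (SoA); the cycle rules of SAP 7.2.1 and 7.3.1. Assumed: menses of 2 to 7 days, and regular cycles until periods stop.

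Day the rule is met = last bleeding day + 56. To be met by Day 85, the last bleeding day must be no later than 85 − 56 = Day 29. To be met by Day 169, it must be no later than 169 − 56 = Day 113.

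Example: 28-day cycle, 5-day menses, first dose on cycle day 1, baseline cycle 28 days. Days follow the SAP numbering, which has no Day 0.

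| Menses after the first-dose one | Last bleeding day | Rule met | Week 6 cycle | Week 12 cycle | Week 24 cycle | Lengths |
|---|---|---|---|---|---|---|
| 0 | 5 | Day 61 | −23 to 5 | −23 to 5 | −23 to 5 | 28, 28, 28 |
| 1 | 33 | Day 89 | 6 to 33 | 6 to 33 | 6 to 33 | 28, 28, 28 |
| 2 | 61 | Day 117 | 6 to 33 | 34 to 61 | 34 to 61 | 28, 28, 28 |
| 3 | 89 | Day 145 | 6 to 33 | 62 to 89 | 62 to 89 | 28, 28, 28 |

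In the first row, 23 + 5 = 28 days, and the change from baseline is 28 − 28 = 0 at all three time points. The selected menses ends 85 − 5 = 80 days before the Week 12 visit and 169 − 5 = 164 days before the Week 24 visit. In the second row the distances are 85 − 33 = 52 and 169 − 33 = 136 days.

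The same rules were applied to every cycle length from 21 to 35 days, menses of 2 to 7 days, and 0 to 3 post-dose menses. Every combination gave an unchanged cycle length at all three time points. This follows from the rules: they select a cycle that ended before the stop.

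**4. What does SAP 4.3 show?** A gap that ends with a new menses is a completed long cycle. With 5-day menses, its length is at least 5 + 56 = 61 days, and it enters the same category as a 36-day cycle. A gap still open at the last diary entry has no completed length, and no rule covers it. Because the period runs from consent, cycles from up to 75 days of screening are pooled with cycles on or after treatment.

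**5. Size.** No figure in the documents bears on this. As an illustration, take 38 women per arm, an assumed true rate p and an assumed fraction c of events reported. Expected reported cases are 38pc, and the chance that the table shows none is (1 − pc)^38.

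| p | c = 100% | c = 50% | c = 25% |
|---|---|---|---|
| 10%: expected cases | 3.8 | 1.9 | 0.95 |
| 10%: chance of none | 1.8% | 14.2% | 38.2% |
| 5%: chance of none | 14.2% | 38.2% | 62.0% |

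Put another way, if 4 of 38 women (10.5%) had the event and 25 to 75% were reported, the table would show 1 to 3 of 38 (2.6 to 7.9%). These values show sensitivity only; they do not estimate an under-count.

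**The case against.** The strongest reply is that capture does not rest on open-ended questions alone. Protocol 8.4.2 calls them only the preferred method. Investigators have the definition and must report AESIs. Sex hormones at Visits 5, 7, 9 and 10 are to be drawn on cycle days 1 to 5, so sites have to follow menses and absent periods would disrupt sampling. Pregnancy tests at the same visits and cycle-timed ultrasound add further prompts. This stands: a reader might infer that the AESI *is* under-counted, and the documents do not show that. They show a risk. None of these prompts is a check of the diary against the 56-day rule; the e-Diary review in the SoA concerns entry compliance.

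A reader might also infer that the cycle tables drop women whose periods stop. The SAP does not say so. Read literally, SAP 7.2.1 and 7.3.1 give such a woman an earlier, normal cycle. In SAP 4.3 she still contributes her completed cycles, and only the open interval goes uncounted. She would be missing from SAP 7.3.6 only if a programmer limited the look-back, for example by the day windows in SAP Table 12.2, which 7.2.1 and 7.3.1 do not invoke.

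It is also true that the diary is not ignored. Heaviness and cycle changes are summarised, and daily scores are listed, so gaps could be recovered by hand. A listing, however, is not a planned comparison by arm. Finally, SAP 4.3 is a descriptive table under baseline information, which makes its gaps secondary to those in SAP 8.1.

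**Conclusion.** The point holds as a risk of under-counting combined with masking. The protocol's rule is objective, the data to apply it are collected daily, and no planned analysis applies it. The cycle summaries cannot substitute: one pools the relevant gaps with much shorter ones and has no place for an open gap, and the other can show zero change for a woman who already meets the rule.

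The masking result assumes regular cycles before periods stop and a literal reading of the closest-menses and latest-menses rules. Using the diary as the source is a reasonable inference, since 10.3.1 does not name it. The size of any under-count cannot be computed from the documents. This is an inexpensive improvement to the analysis of a named risk. It is not a contradiction in the plan or a demonstrated bias.

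**What to change.** **SAP 8.1.** Beside the reported AESI, add the number and percentage of women per arm with at least one run of 56 or more consecutive days without bleeding or spotting, after first dose and through the last diary entry. Exclude pregnancy. Count a run that is still open at the last entry once it reaches 56 days. Show runs containing missing diary days separately. Reconcile the result with the reported AESIs.

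**SAP 4.3.** Report screening and post-dose cycles separately. Keep the cycle in progress at first dose in the post-dose set. Dosing falls on cycle days 1 to 5, so a rule limited to cycles starting on or after first dose would lose a woman dosed on days 2 to 5 who never bleeds again. Show unfinished cycles as censored, not as completed lengths.

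**SAP 7.3.6.** Flag Week 6, 12 and 24 measurements whose selected menses lies before first dose or beyond a stated distance from the visit. As a guide, a regular 35-day cycle with 2-day menses has 33 bleeding-free days. The closest menses is then at most 17 days from a visit, and the latest earlier one at most 33 days.

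**Cost.** SAP wording, one derivation from data already collected and two flags. The real work is agreeing the rule for missing diary days and the distance limit before unblinding. No study procedure changes.

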10.3.2 Definition of SAE

If an event is not an AE per definition above, then it cannot be an SAE even if serious conditions are met.

An SAE is defined as any untoward medical occurrence that, at any dose:

a. Results in death

b. Is life-threatening

The term 'life-threatening' in the definition of 'serious' refers to an event in which the subject was at risk of death at the time of the event. It does not refer to an event, which hypothetically might have caused death, if it were more severe.

Version 6.0 83 of 138 April 11, 2024

c. Requires inpatient hospitalization or prolongation of existing hospitalization

- In general, hospitalization signifies that the subject has been detained (usually involving at least an overnight stay) at the hospital or emergency ward for observation and/or intervention that would not have been appropriate in the physician's office or outpatient setting. Complications that occur during hospitalization are AEs. If a complication prolongs hospitalization or fulfills any other serious criteria, the event is serious. When in doubt as to whether "hospitalization" occurred or was necessary, the AE should be considered serious.
- Hospitalization for elective intervention of a pre-existing condition that did not worsen from Baseline is not considered an AE.

d. Results in persistent disability/incapacity

- The term disability means a substantial disruption of a person's ability to conduct normal life functions.
- This definition is not intended to include experiences of relatively minor medical significance such as uncomplicated headache, nausea, vomiting, diarrhea, influenza, and accidental trauma (e.g., sprained ankle) which may interfere with or prevent everyday life functions but do not constitute a substantial disruption.

e. Is a congenital anomaly/birth defect

f. Other situations

- Medical or scientific judgment should be exercised in deciding whether SAE reporting is appropriate in other situations such as important medical events that may not be immediately life-threatening or result in death or hospitalization but may jeopardize the subject or may require medical or surgical intervention to prevent one of the other outcomes listed in the above definition. These events should usually be considered serious.
- Examples of such events include invasive or malignant cancers, intensive intervention in an
 emergency room or at home for allergic bronchospasm, blood dyscrasias or convulsions that
 do not result in hospitalization, or development of drug dependency or drug abuse.

10.3.3 Recording and Follow-up of AE and SAE

AE and SAE Recording

When an AE/SAE occurs, it is the responsibility of the Investigator to review all
documentation (e.g., hospital progress notes, laboratory, and diagnostics reports) related to
the event.

Version 6.0 84 of 138 April 11, 2024

- The Investigator will then record all relevant AE/SAE information in the eCRF.
- It is **not** acceptable for the Investigator to send photocopies of the subject's medical records to the Sponsor in lieu of completion of the AE/SAE eCRF page.
- There may be instances when copies of medical records for certain cases are requested by the Sponsor. In this case, all subject identifiers, with the exception of the subject number, will be blinded on the copies of the medical records before submission to the Sponsor.
- The Investigator will attempt to establish a diagnosis of the event based on signs, symptoms, and/or other clinical information. In such cases, the diagnosis (not the individual signs/symptoms) will be documented as the AE/SAE.
- Adverse event questioning will include specific questions regarding symptoms of COVID-19: fever, cough, dry throat, difficulty breathing.
- Confirmed and suspected SARS-CoV-2 infection and COVID-19 will be recorded as AEs.

Assessment of Intensity

The Investigator will make an assessment of intensity for each AE and SAE reported during the study and assign it to one of the following categories:

- Mild: An event that is easily tolerated by the subject, causing minimal discomfort and not interfering with everyday activities.
- Moderate: An event that causes sufficient discomfort and interferes with normal everyday activities.
- Severe: An event that is incapacitating with inability to work or do normal everyday
 activities. An AE that is assessed as severe should not be confused with an SAE. Severe is a
 category utilized for rating the intensity of an event; and both AE and SAE can be assessed
 as severe.

An event is defined as 'serious' when it meets at least one of the predefined outcomes as described in the definition of an SAE, NOT when it is rated as severe.

Assessment of Causality

- The Investigator is obligated to assess the relationship between study intervention and each occurrence of each AE/SAE.
- The Investigator will use the following definitions to assess the relationship of the adverse event to the use of study intervention:

Version 6.0 85 of 138 April 11, 2024

Reasonable Possibility:

After consideration of factors including timing of the event, biologic plausibility, clinical judgment, and potential alternative causes, there is **sufficient** evidence (information) to suggest a causal relationship.

No Reasonable Possibility:

After consideration of factors including timing of the event, biologic plausibility, clinical judgment, and potential alternative causes, there is **insufficient** evidence (information) to suggest a causal relationship.

- For causality assessments, events assessed as having a reasonable possibility of being related to the study intervention will be considered "associated." Events assessed as having no reasonable possibility of being related to study intervention will be considered "not associated." When the event is causality assessment impossible and cannot rule out causality, e.g., insufficient case data, the event will also be considered associated and revised if appropriate when accessible.
- Alternative causes, such as underlying disease(s), concomitant therapy, and other risk factors, as well as the temporal relationship of the event to study intervention administration will be considered and investigated.
- The Investigator will also consult the Investigator's Brochure and/or Product Information, for marketed products, in his/her assessment.
- For each AE/SAE, the Investigator must document in the medical notes that he/she has reviewed the AE/SAE and has provided an assessment of causality.
- There may be situations in which an SAE has occurred, and the Investigator has minimal information to include in the initial report to the Sponsor. However, it is very important that the Investigator always make an assessment of causality for every event before the initial transmission of the SAE data to Sponsor.
- The Investigator may change his/her opinion of causality in light of follow-up information and send an SAE follow-up report with the updated causality assessment.
- The causality assessment is one of the criteria used when determining regulatory reporting requirements.

Version 6.0 86 of 138 April 11, 2024

Follow-up of AE and SAE

- The Investigator is obligated to perform or arrange for the conduct of supplemental measurements and/or evaluations as medically indicated or as requested by the Sponsor to elucidate the nature and/or causality of the AE or SAE as fully as possible. This may include additional laboratory tests or investigations, histopathological examinations, or consultation with other health care professionals.
- During the course of the study, new or updated information will be recorded in the
 originally completed eCRF. The Investigator will submit any updated SAE data to the
 Sponsor within 24 hours of receipt of the information.
- Any AEs that are unresolved at last visit in the study are followed up by the Investigator
 for as long as medically indicated but without further recording in eCRF. For any subject
 with ongoing AE(s)/SAE(s) at the end of the study, the Sponsor retains the right to request
 additional information if judged necessary.

